## 5. STATISTICAL CONSIDERATIONS

### 5.1 Sample Size

[figure not shown]
Our sample size calculations are based on pairwise comparisons of screening rates and used preliminary data from the KPWA electronic medical record and observed data from the prior HOME trial. Using 2019 KPWA cervical cancer screening data, we estimate 37.1% of screening-adherent, 30.8% of Overdue, and 27.8% of individuals with Unknown screening histories will be screened within 6 months of randomization in the Education arm. Calculations assume a two-sided level 0.05 test, for differences in two proportions.

Our sample size was selected for adequate power to detect meaningful differences in cervical cancer screening rates between outreach strategies within each of the 3 target populations. Meaningful differences were selected based on estimates from the literature and observed data from the HOME trial. Small improvements in screening uptake are important, particularly if cost-effective and patient-centered; thus, the study is powered to detect relatively small differences between groups. Based on prior studies, we anticipate the Direct Mail strategy will have a greater impact on screening uptake than the Opt-In approach compared to Education; therefore, we have powered the study for a larger minimal detectable difference for the Direct Mail effect.

We estimated the sample size necessary to have 80% power to detect a 3% difference between Opt-In and Education and a 5% difference in screening completion between Direct Mail and Education. We anticipate that the Direct Mail strategy will have a larger impact on screening outcomes than the Opt-In approach, therefore we selected a larger detectable difference (and thus a smaller sample size needed)

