for the Direct Mail group. However, in the screening-adherent population, we computed the sample sizes needed for the 3% and 5% detectable differences respectively, and based the Education arm on the sample size necessary for the Education versus Opt-In comparison, which was larger than necessary for the Education versus Direct Mail comparison. Thus, we will have 80% power to detect a 4.1% difference for the Education vs. Direct Mail screening completion comparison. We selected sample size in the Usual Care group to detect a difference of 3.0% in screening completion between Usual Care and Education for the Screening-Adherent and Unknown populations. Given the smaller sample sizes in the intervention groups for the Overdue population, we were unable to achieve a least detectable difference (LDD) of 3.0% between Usual Care and Education. With a sample size of N=1398 in the Education group (based on an LDD of 3% for Education vs Direct Mail), we computed the detectable difference for a variety of sample sizes for the Usual Care group. We selected a sample size of N=5592 (4 Usual Care participants for each Education participant), because further increasing the Usual Care group led to diminishing improvements in LDD. This sample size yields a least detectable difference of 3.8%.

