**FIGURE 3: STEP randomization allocation by screening history**

Target sample sizes for each group, stratified by screening history, are shown in Figure 3, and will include randomizing a total of 13,735 Screening-Adherent (3879 Usual Care, 4171 Education, 4171 Opt-In, and 1514 Direct Mail); 8388 Overdue (5592 Usual Care, 1398 Education, and 1398 Direct mail); and 10,500 Unknown (3128 Usual Care, 3686 Education, and 3686 Opt-In).

Study enrollment will occur over a 14-month recruitment period. For all three study populations (Screening-Adherent, Overdue, and Unknown), the number of eligible individuals is estimated to exceed the number needed for the study. Therefore, to reach target sample size over the recruitment period, we will randomly select 231 Screening-Adherent, 142 Overdue, and 1777 Unknown individuals from the pool of all eligible individuals each week, for inclusion in the study. We will allocate each weekly sample to randomization groups as follows: Screening-Adherent (65 Usual Care, 70 Education, 70 Opt-In, and 26 Direct Mail), Overdue (94 Usual Care, 24 Education, and 24 Direct Mail), and Unknown (53 Usual Care, 62 Education, and 62 Opt-In). This sampling strategy maintains a consistent distribution across randomization arms over time, minimizing any potential impacts of temporal trends on group comparisons. If the number of eligible individuals in any given week is lower than the weekly target, the shortfall will be added to the target recruitment sample for the following week.

Beginning with wave 43, each randomization group (except Usual Care) will be further stratified by  $\leq 45$  years and  $>45$  years age groups, and then 1:1 randomized to receive age-targeted or non-age-targeted optimized Education brochure as part of their intervention materials (see Figure 2).

Our sample size estimates were based on data from 2019, before the COVID-19 pandemic which has impacted in-person cervical cancer screening. The sample size and recruitment plan described above is our *a priori* sampling strategy to achieve target sample size over the 14-month recruitment period. However, since the number of eligible individuals will vary with each data pull, and may be impacted by changes to care delivery, we will closely monitor recruitment and make necessary changes to ensure target sample sizes are met. Potential changes include the following:

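### Section 5.1 labels the Overdue Education arm (N=1398) with a 3% detectable difference when it delivers 5%, and prints a weekly Unknown draw of 1777 when its arms sum to 177

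*Combined protocol and SAP*

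**What the plan says.** Protocol Section 5.1 gives the inputs. On the test: "Calculations assume a two-sided level 0.05 test, for differences in two proportions". On the Education-arm rates: "we estimate 37.1% of screening-adherent, 30.8% of Overdue, and 27.8% of individuals with Unknown screening histories will be screened within 6 months". On the design targets: "80% power to detect a 3% difference between Opt-In and Education and a 5% difference in screening completion between Direct Mail and Education". The section explains that Direct Mail is expected to have the larger effect, and was therefore given a larger detectable difference and a smaller sample.

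Further on, when it derives the Overdue Usual Care arm, the section states: "With a sample size of N=1398 in the Education group (based on an LDD of 3% for Education vs Direct Mail"). It then chooses 5592 for Usual Care and reports a detectable difference of 3.8% against Education. The Overdue targets are "8388 Overdue (5592 Usual Care, 1398 Education, and 1398 Direct mail").

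The text below the Figure 3 heading, still in Section 5.1, sets the weekly draws: 231 Screening-Adherent, then "142 Overdue, and 1777 Unknown individuals from the pool of all eligible individuals each week". The next sentence splits each weekly sample by arm, and for the third population gives "Unknown (53 Usual Care, 62 Education, and 62 Opt-In").

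**The concern.** The same contrast, Direct Mail versus Education, carries two detectable differences in one section: 5 points as the design target and 3 points as the basis of the Overdue arm size. The Overdue population has no Opt-In arm, so the 3-point Opt-In target cannot explain the second figure. Section 5.3.1 leaves Usual Care out of the primary analysis, which makes Direct Mail versus Education the only pairwise primary contrast in this population. Section 5.1 also says that small gains in uptake matter. A reader who takes the 3% at face value would treat a null result as evidence against a 3-point gain that the trial is more likely than not to miss.

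The weekly Unknown figure is about ten times the sum of the arms it feeds. It matters beyond tidiness because Section 5.1 carries any shortfall against the weekly target into the next week, and because changes to the recruitment plan depend on how eligible numbers compare with that target.

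**Working it through.** **Inputs, all from Section 5.1.** Overdue Education rate p1 = 0.308; two-sided alpha 0.05 (z = 1.960); power 80% (z = 0.842); 1398 in each of Education and Direct Mail. The section states no inflation for dropout or for clustering by provider, so none is applied.

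**Formula** (two proportions, equal arms, pooled variance under the null, pbar the mean of p1 and p2, d = p2 − p1):

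n per arm = [1.960 × √(2·pbar·(1−pbar)) + 0.842 × √(p1(1−p1) + p2(1−p2))]² / d²

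**Reproducing 1398 with 5 points** (0.308 vs 0.358, pbar = 0.333):
- 1.960 × √0.4442 = 1.3063
- 0.842 × √0.4430 = 0.5602
- (1.3063 + 0.5602)² / 0.05² = 3.484 / 0.0025 ≈ 1,394

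The plan's 1398 is within 0.3% of this. An unpooled variance gives 1,391 and a continuity correction gives 1,434.

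**The same formula with 3 points** (0.308 vs 0.338, pbar = 0.323):
- 1.960 × √0.4373 = 1.2962
- 0.842 × √0.4369 = 0.5563
- (1.2962 + 0.5563)² / 0.03² = 3.432 / 0.0009 ≈ 3,813

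That is 3,813 / 1,398 = 2.7 times the planned arm. No variant rescues the label: the requirement is 3,811 unpooled, 3,880 with continuity correction and 3,612 if the difference is a decrease. Even a one-sided test of a decrease needs 2,846.

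**Power at 1398 per arm** = Φ[(d√1398 − 1.960√(2·pbar·(1−pbar))) / √(p1(1−p1) + p2(1−p2))]:
- 3 points: Φ[(1.1217 − 1.2962) / 0.6610] = Φ(−0.264) = 39.6%
- 5 points: Φ[(1.8695 − 1.3063) / 0.6656] = Φ(0.846) = 80.1%

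Solving for 80% power gives a detectable difference of 4.99 points.

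**Is this the plan's method?** The same calculation recovers the section's other detectable differences, taking Usual Care below Education where it is involved:

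| Comparison | Arms | Plan | Recomputed |
|---|---|---|---|
| Adherent, Education vs Direct Mail | 4171 / 1514 | 4.1% | 4.09 |
| Overdue, Education vs Usual Care | 1398 / 5592 | 3.8% | 3.78 |
| Adherent, Education vs Usual Care | 4171 / 3879 | 3.0% | 2.99 |
| Unknown, Education vs Usual Care | 3686 / 3128 | 3.0% | 3.00 |
| Overdue, Education vs Direct Mail | 1398 / 1398 | 3% | 4.99 |

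Only the last row fails. The section's own text points the same way: if 1398 against 5592 detects no less than 3.8 points, 1398 against 1398 cannot detect 3.

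**Weekly draws against their arm sums and population targets:**

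| Population | Printed draw | Sum of arms | Weeks to target |
|---|---|---|---|
| Screening-Adherent | 231 | 65+70+70+26 = 231 | 13,735 / 231 = 59.5 |
| Overdue | 142 | 94+24+24 = 142 | 8,388 / 142 = 59.1 |
| Unknown | 1777 | 53+62+62 = 177 | 10,500 / 177 = 59.3; 10,500 / 1777 = 5.9 |

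Fourteen months is about 61 weeks (14 × 365.25 / 12 / 7 = 60.9). At 1777, 1777 − 177 = 1,600 people a week would have no arm.

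**The case against.** The strongest reply is that both are slips whose correct values stand nearby. The main power statement, "a 5% difference in screening completion between Direct Mail and Education", is right. The 3% sits in a parenthesis, in a sentence whose purpose is to size Usual Care, and no arm size, test or other detectable difference depends on it. Results will be reported as relative risks with robust standard errors, so the interval, rather than the planned detectable difference, would show what a null result excludes. For the weekly draw, the arm split follows at once, and all totals fit 177 (13,735 + 8,388 + 10,500 = 32,623, the planned enrolment in Section 5.2). A tenfold draw could hardly be carried out unnoticed.

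Much of this stands. N=1398 is sound, nothing downstream is contaminated, and the documents do not show that anyone sampled at 1777 a week. The misreading of a null result is a risk, not a planned inference. But the reply does not make either printed figure correct. Section 5.1 gives two detectable differences for one primary contrast, and the reader must recalculate to learn which one the arm size supports. The weekly number is a stated sampling target with a carry-over rule attached.

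**Conclusion.** Both figures are wrong as written. At 1398 per arm the Overdue Direct Mail versus Education comparison has a detectable difference of 5 points (4.99) at 80% power; at the labelled 3 points its power is 39.6%, about half the nominal level. The weekly Unknown draw should equal its arm sum of 177; the printed 1777 is ten times too large. The first result rests on the plan's 30.8% Education rate, a two-sided 0.05 test, and no allowance for clustering or dropout, as in the plan. The second is addition. Figure 3 was not available for this check, but both contradictions lie within the text. The likely cause is typographical, and the design itself is internally consistent once the two numbers are corrected.

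**What to change.** In Section 5.1, restate the basis of the Overdue Education arm as a detectable difference of 5% for Education versus Direct Mail (30.8% vs 35.8%, 80% power), in line with the target given earlier in the section. Change the weekly Unknown draw from 1777 to 177, and confirm against the sampling records that 177 was the working target. Check that Figure 3 and any report or manuscript drawing on this section carry the corrected values.

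The cost is two number corrections. The Overdue parenthesis becomes less favourable than printed, but it then agrees with the design target already stated. No arm size, enrolment total or analysis changes.

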**FIGURE 3: STEP randomization allocation by screening history**

Target sample sizes for each group, stratified by screening history, are shown in Figure 3, and will include randomizing a total of 13,735 Screening-Adherent (3879 Usual Care, 4171 Education, 4171 Opt-In, and 1514 Direct Mail); 8388 Overdue (5592 Usual Care, 1398 Education, and 1398 Direct mail); and 10,500 Unknown (3128 Usual Care, 3686 Education, and 3686 Opt-In).

Study enrollment will occur over a 14-month recruitment period. For all three study populations (Screening-Adherent, Overdue, and Unknown), the number of eligible individuals is estimated to exceed the number needed for the study. Therefore, to reach target sample size over the recruitment period, we will randomly select 231 Screening-Adherent, 142 Overdue, and 1777 Unknown individuals from the pool of all eligible individuals each week, for inclusion in the study. We will allocate each weekly sample to randomization groups as follows: Screening-Adherent (65 Usual Care, 70 Education, 70 Opt-In, and 26 Direct Mail), Overdue (94 Usual Care, 24 Education, and 24 Direct Mail), and Unknown (53 Usual Care, 62 Education, and 62 Opt-In). This sampling strategy maintains a consistent distribution across randomization arms over time, minimizing any potential impacts of temporal trends on group comparisons. If the number of eligible individuals in any given week is lower than the weekly target, the shortfall will be added to the target recruitment sample for the following week.

Beginning with wave 43, each randomization group (except Usual Care) will be further stratified by  $\leq 45$  years and  $>45$  years age groups, and then 1:1 randomized to receive age-targeted or non-age-targeted optimized Education brochure as part of their intervention materials (see Figure 2).

Our sample size estimates were based on data from 2019, before the COVID-19 pandemic which has impacted in-person cervical cancer screening. The sample size and recruitment plan described above is our *a priori* sampling strategy to achieve target sample size over the 14-month recruitment period. However, since the number of eligible individuals will vary with each data pull, and may be impacted by changes to care delivery, we will closely monitor recruitment and make necessary changes to ensure target sample sizes are met. Potential changes include the following:

- 1) If the number of eligible individuals is consistently below the weekly target sample size, we will consider randomizing all eligible individuals rather than a sample, during weeks where there are more eligible individuals than the weekly target. The allocation fractions to randomization groups would remain the same as the original recruitment plan.
- 2) Since our comparison between Usual Care and Education is an exploratory aim, if the number of eligible individuals is considerably lower than anticipated, we will consider reducing the sample size allocated to Usual Care, to ensure target sample sizes in the Education, Opt-In, and Direct Mail groups are met.

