All analyses will be stratified by screening history population (Adherent, Overdue, and Unknown). All analyses will be based on the intention to treat principle, with individuals analyzed by the outreach approach arm to which they were randomly assigned. We will first conduct an overall chi-square test to assess differences in observed screening rates among randomization groups. The primary analysis will use a modified Poisson regression modeling approach to estimate the relative risk of screening completion associated with Direct Mail, and Opt-In strategies relative to Education (as appropriate by screening history population). A binary indicator for screening completion within 6 months (yes/no), as defined above, will be the dependent variable. Models will be fit using generalized estimating equations with an independent working correlation structure and robust standard error estimation to account for correlation between participants paneled to the same primary care provider. Models will adjust for baseline characteristics that differ by randomization arm. Models for Overdue participants will also be adjusted for overdue duration (<3 years and  $\geq 3$  years). The analysis for the outcome of screening initiation will use the same methods. The primary analysis will not include the Usual Care group, but secondary analyses will include this group, and will estimate the relative risk of screening outcomes for Education, relative to Usual Care.

Delays in screening impact time in compliance with screening recommendations and can also impact cancer outcomes. Thus, our analysis will also assess the time it takes to complete screening, defined as the number of days between randomization and screening completion, as a secondary outcome. We will use Kaplan-Meier log-rank tests to compare time to screening completion by randomization arm, with follow-up time censored at 6 months for non-completers. Analyses will be stratified by screening history population (Adherent, Overdue, and Unknown).

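### Usual Care allocation may be cut during recruitment, and no described model adjusts Education versus Usual Care for randomization wave, so a time trend could bias that secondary comparison

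*Combined protocol and SAP*

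**What the plan says.** Section 5.1 sets fixed weekly counts per arm. Education to Usual Care is 70 to 65 in Screening-Adherent, 24 to 94 in Overdue and 62 to 53 in Unknown. The stated reason is: "This sampling strategy maintains a consistent distribution across randomization arms over time, minimizing any potential impacts of temporal trends on group comparisons".

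The same section then lists two possible changes if recruitment falls short. The first, randomizing everyone eligible in the fuller weeks, explicitly keeps the allocation fractions. The second does not: "we will consider reducing the sample size allocated to Usual Care", so that Education, Opt-In and Direct Mail still reach target. It gives no size, timing or analytic consequence for the cut.

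On analysis, Section 5.3.1 says: "Models will adjust for baseline characteristics that differ by randomization arm". The Overdue models also adjust for overdue duration. The Education versus Usual Care comparison is a secondary analysis reported as a relative risk. The brochure sub-study model (wave 43 onward) has indicators for Usual Care and the two brochure types; screening history and age enter only in secondary interaction models. Section 5.3.2 adds a cost-effectiveness ratio for Education against Usual Care. Wave, week and calendar time are named in none of these.

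**The concern.** With a constant weekly ratio, a trend in screening completion affects both arms equally and cancels. Once Usual Care alone is cut part-way through, its participants come disproportionately from earlier waves and Education's from later ones. A model without a time term then reads part of any trend as an effect of the educational materials.

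A trend is plausible on the protocol's own account. Section 4.1.1 describes a halt in routine screening from March to August 2020, a backlog, and a 12-month deferral of people due in that window. Section 5.1 says that the planning rates predate the pandemic, which has affected in-person screening. A disruption in care delivery could both lower eligible numbers, which triggers the contingency, and shift completion rates.

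At stake are the estimate of what the educational materials do on their own and the corresponding cost-effectiveness ratio. Usual Care was sized for this comparison and takes 3,879 + 5,592 + 3,128 = 12,599 of the 32,623 planned participants.

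**Working it through.** **Inputs from Section 5.1.** "Calculations assume a two-sided level 0.05 test, for differences in two proportions". Power is 80%. Education-arm rates: "we estimate 37.1% of screening-adherent, 30.8% of Overdue, and 27.8% of individuals with Unknown screening histories will be screened within 6 months". Arm sizes (Education, Usual Care): 4171 and 3879 Adherent; 1398 and 5592 Overdue; 3686 and 3128 Unknown.

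**The plan's own figures.** For Adherent and Unknown: "We selected sample size in the Usual Care group to detect a difference of 3.0% in screening completion between Usual Care and Education". For Overdue: "This sample size yields a least detectable difference of 3.8" percent. I used the pooled-variance test of two proportions, with Usual Care below Education. For Overdue at 30.8% versus 27.0%:

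- pooled rate = 0.2 × 0.308 + 0.8 × 0.270 = 0.2776
- null SE = √[0.2776 × 0.7224 × (1/5592 + 1/1398)] = 0.01339
- alternative SE = √[0.308 × 0.692/1398 + 0.270 × 0.730/5592] = 0.01370
- z = (0.038 − 1.96 × 0.01339)/0.01370 = 0.86, so power is about 80.5%

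The 3.8-point figure is reproduced. At 3.0 points, power is 80.2% in Adherent and 80.0% in Unknown. These differences are sound yardsticks for the bias.

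**Bias formula.** Assume no education effect. Let the mean completion rate differ by d between two recruitment periods, equally in both arms. Let s be the share of an arm's participants who come from the later period. Then

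crude bias = (s for Education − s for Usual Care) × d.

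- No cut: the shares are equal, so the bias is 0.
- Usual Care halved for the second half: s = 1/2 for Education and 0.5/(1 + 0.5) = 1/3 for Usual Care, so the bias is d/6.
- Usual Care halved for the last 30% of recruitment: s = 0.30 and 0.15/0.85 = 0.176, so the bias is 0.124d.

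The starting ratio cancels. The formula is therefore the same in each population for the same relative cut and trend, provided weekly Education numbers stay constant.

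**Numbers in.** The values of d and the cut are assumed.

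| d (points) | Bias, halved for second half | Bias, halved for last 30% | Actual error of nominal 5% test, halved for second half |
|---|---|---|---|
| 3 | 0.50 | 0.37 | 7% Adherent and Unknown, 6.5% Overdue |
| 5 | 0.83 | 0.62 | 11% Adherent and Unknown, 9% Overdue |
| 10 | 1.67 | 1.24 | 30% Adherent and Unknown, 22% Overdue |

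Worked case, Adherent with d = 5, so rates of 34.6% then 39.6%: Education averages 37.1%, and Usual Care averages (2/3) × 34.6 + (1/3) × 39.6 = 36.27%. The difference is 0.83 points and the spurious relative risk is 37.1/36.27 = 1.023. If rates fall instead, every sign reverses. The value d is the gap between period means: under a steady linear trend split at the midpoint, it is half the total change over recruitment.

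**With adjustment.** Under no effect, the arms have equal rates within each period, so a comparison stratified by period has zero bias. For Usual Care halved at mid-recruitment and d = 5, the standard error of the difference moves from 1.17 (crude) to 1.18 points (stratified, Mantel-Haenszel weights) in Adherent, from 1.17 to 1.19 in Unknown, and from 1.41 to 1.43 in Overdue.

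**The case against.** The strongest reply is that this is a chain of conditions. Section 5.1 expects eligible numbers to exceed need in all three populations, and a cut is only to be considered. Bias needs the trigger, a decision to cut, a cut after the first wave, a real trend, and no adjustment for time. A cut applied from the first wave produces none. The deferral in Section 4.1.1 is itself meant to lessen pandemic distortion. The comparison is secondary, and the contingency itself calls it exploratory. All of this stands. It limits the weight of the point without supplying the missing safeguard.

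A second reply is that adjustment for characteristics that differ by arm could pick up enrollment period after a cut. It could, but the rule depends on the data and does not name wave, so it cannot be counted as planned protection.

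A third is that Section 5.3.1 defers further detail to a SAP. No separate SAP text is in the document reviewed, so the absence of a time term is established only for the models described there.

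A reader might also infer a larger problem: bias that matches or exceeds the detectable difference. With Usual Care stopped at mid-recruitment the formula gives d/2, or 5.0 points at d = 10. The documents do not support that reading. They speak of reducing Usual Care, not ending it, and they give no trend of any size or direction.

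**Conclusion.** The gap is real but conditional. The plan names constant allocation as its protection against time trends, permits that protection to be removed for Usual Care alone, and describes no model that replaces it. If the contingency is used mid-recruitment while completion rates are moving, Education versus Usual Care and its cost-effectiveness ratio could be biased in the direction of the trend. Halving Usual Care for the second half gives about 0.5 to 1.7 points for assumed shifts of 3 to 10 points. That is below the 3.0 and 3.8 points the comparison is sized to detect, but enough to raise the false-positive rate above 5%.

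It would be wrong to infer that the main results are threatened. The contingency leaves Education, Opt-In and Direct Mail at target, and the primary analysis excludes Usual Care. The sub-study is exposed only to ratio changes from wave 43 onward. Nor do the documents say that the contingency was used.

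**What to change.** Add to Section 5.3.1 (and the SAP) that every Education versus Usual Care analysis is adjusted for, or stratified by, randomization wave or calendar month. This covers the secondary relative-risk models, the wave-43-onward sub-study model and the Education versus Usual Care cost-effectiveness ratio. For the ratio, compute incremental cost and incremental completion within the same periods and with the same weights.

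Add to the second contingency in Section 5.1 that any change in the Usual Care fraction is recorded by wave. After such a change, the comparison is made within periods of concurrent allocation and combined across them. If month is the time term, it should be split where the fraction changes.

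Allocation is already done by week, so no new data are needed. The cost is a few degrees of freedom against, for example, 4171 + 3879 = 8050 participants in the Adherent comparison. Precision is nearly unchanged for a moderate cut and suffers noticeably only if the cut is severe. In the limiting case of no Usual Care after mid-recruitment, the Adherent standard error would rise from 1.32 to 1.50 points.
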